#### 3. Subject Selection

## 3.1 Intended use population

The intended use population for the mt-sRNA test will include men and women who are 45 or older and are of average-risk for development of colorectal cancer and are asymptomatic of gastrointestinal symptoms that would warrant a diagnostic colonoscopy. To increase the point prevalence of CRC in subjects recruited for the study, subject enrollment will include the following:

- Inclusion of individuals with a family history of colorectal cancer
- Enrichment of the 65 and older age range, provided it does not exceed 60% of the total study population

# 3.2 Eligibility Criteria

#### **Inclusion Criteria:**

- Subject is male or female, >45 years of age
- Subject is able to understand the study procedures, and is able to provide consent to participate in the study and authorizes release of relevant protected health information through reviewing and consenting to a HIPAA medical release form

GENEOSCOPY,	INIC
deliteoscol 1,	IIVC.

**Document Number: VAL-PRT-0041** 

• Subject is able and willing to provide stool samples prior to a colonoscopy procedure.

• Subject is able and willing to undergo a colonoscopy after providing a stool sample

#### **Exclusion Criteria:**

- Subject had any precancerous findings on most recent colonoscopy. This does not include benign, and/or hyperplastic polyps of any size (Note: Tissue biopsies that result in no histopathology findings are acceptable)
- Subject has a history or diagnosis of colorectal cancer
- Subject has a history of aerodigestive tract cancer
- Subject has had a positive non-invasive screening diagnostic within the associated recommended intervals
  - Fecal occult blood test or fecal immunochemical test within the previous twelve (12) months
  - FIT-DNA test within the previous 36 months
- Subject has had a colonoscopy in the previous nine (9) years.
- Subject has had a prior colorectal resection for any reason other than sigmoid diverticular disease
- Indication for colonoscopy was due to overt rectal bleeding, e.g., hematochezia or melena, within the previous 30 days. (Blood on toilet paper, after wiping, does not constitute rectal bleeding)
- Subject has a diagnosis or personal history of any of the following high-risk conditions for colorectal cancer:
  - o Inflammatory bowel disease (IBD) including chronic ulcerative colitis (CUC) and Crohn's disease
  - o Familial adenomatous polyposis (also referred to as "FAP", including attenuated FAP)
  - Hereditary non-polyposis colorectal cancer syndrome (also referred to as "HNPCC" of "Lynch Syndrome")
  - Other hereditary cancer syndromes including but are not limited to Peutz-Jeghers Syndrome, MYH-Associated Polyposis (MAP), Gardner's Syndrome, Turcot's (or Crail's) Syndrome, Cowden's Syndrome, Juvenile Polyposis, Cronkhite-Canada Syndrome, Neurofibromatosis and Familial Hyperplastic Polyposis

#### 3.3 Criteria for withdrawal

Subjects who enroll into the study but do not complete study requirements will be withdrawn from the analysis. Reasons for withdrawal include:

- Withdrew consent to participate in study
- Inadequate prep
- Inadequate procedure
- Inadequate records
- Inadequate specimen/sample
- Inadequate stool sample
- Inadequate FIT
- Review of eligibility criteria
- Process validation
- Ouantification failure
- Other Processing failure

#### 3.4 Inclusion of Women and Minorities

• Both men and women and members of all races and ethnic groups are eligible for this trial

Title: CRC-PREVENT Clinical Validation Protocol

**Document Number: VAL-PRT-0041** 

# 3.5 Sample Size Requirements

The overall sample size is driven by the need to obtain enough CRC cases so that the lower 95% exact confidence limit for the sensitivity is at least 80%. Table 2 shows the smallest number of CRC cases that would meet this condition for each of 0 - 5 False Negatives.

Table 2. Cases to meet primary objective criteria

Number of CRC Cases	# False Negative	Observed Sensitivity	Lower 95% CL	Upper 95% CL
17	0	100.0%	80.5%	100.0%
26	1	96.2%	80.4%	99.9%
34	2	94.1%	80.3%	99.3%
41	3	92.7%	80.1%	98.5%
48	4	91.7%	80.0%	97.7%
55	5	90.9%	80.0%	97.0%

A sample size of 48 would allow up to 4 false negatives corresponding to an observed sensitivity of 91.7%. Assuming a prevalence of 0.6% in the intended use population, a starting sample size of 8,500 will have 68% chance of yielding at least 48 CRC cases. Given the low prevalence of CRC cases, a small difference between the actual prevalence and the postulated prevalence could lead to too few CRC cases.

The number of CRC cases will be tracked by unblinded study members at the CRO to determine when to stop enrollment. Enrollment will be arrested when a sufficient number of confirmed cases of colorectal cancer have been identified among the cohort to achieve study endpoints. To assess cessation of enrollment, an initial 8,500 participants will be recruited into the study. After this initial enrollment the number of confirmed CRC cases will be assessed against the required number of CRC cases by unblinded study members. If the total number of required cases have not been met after recruitment of 8,500 patients, additional participants will be recruited in 1,000-patient intervals. Enrollment will continue until all endpoints are fully powered.

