## 4.3 Enrollment onto the study

During the official enrollment period, for participants who are considered eligible for the study based on the initial questionnaire and follow-up conversation, the call center at the CRO will contact the participant. The participant will be asked to confirm their identity against the details provided in the online screener by providing their full legal name and date of birth. During this call, the study member will share additional information about the study, including a copy of the Informed Consent Form (ICF) via email and / or text message. The participant will also be asked whether or not they have had sufficient time to read, understand and ask questions about this study and ICF. The participant may take as much time as they would like to read, understand and ask questions about this study and ICF. Additionally, the participant may ask the study member to read the entire ICF over the phone. During enrollment, a study member will discuss the risks and benefits of the study, answer any questions the patient may have about participation, and collect additional details for eligibility.

If the participant decides to enroll onto the study, the participant will consent to enrollment using a secure online signature platform. In the online signature platform, the participant will be asked to sign the informed consent form (ICF) as well as sign required medical data release forms for releasing colonoscopy and histopathology results. A participant will be considered enrolled after understanding and signing the ICF.

During enrollment, the subject will be assigned a unique subject identifier number that will permit deidentification of the subject through the entirety of the study. Whether the participant chooses to provide consent to participate or declines to participate, the participant's response will be recorded and saved for study documentation in the Trial Master File and subject to the Data Management Plan.

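### The 68% chance of 48 CRC cases assumes 8,500 evaluable participants but is attached to 8,500 recruited, and the count that ends enrollment does not require a valid mt-sRNA result

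*Protocol*

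**What the plan says.** Protocol 3.5 (Sample Size Requirements) targets 48 CRC cases, which allows 4 false negatives. It assumes 0.6% prevalence and states that "a starting sample size of 8,500 will have 68% chance of yielding at least 48 CRC cases". SAP 6 repeats the 68% for a starting sample of 8,500.

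The protocol makes that number a recruitment figure: "an initial 8,500 participants will be recruited into the study". If cases are short, "additional participants will be recruited in 1,000-patient intervals". SAP 6 repeats neither of these statements. Protocol 4.3 fixes when enrollment occurs: "A participant will be considered enrolled after understanding and signing the ICF". This comes before the kit, the stool sample and the colonoscopy.

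Losses after consent are foreseen. Protocol 3.3 says: "Subjects who enroll into the study but do not complete study requirements will be withdrawn from the analysis". Protocol 5.3 leaves samples without a result out of the analysis. SAP 5.1 and 7.2 admit a subject to the primary analysis only with both a valid mt-sRNA score and a valid colonoscopy category.

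On stopping, the protocol says: "The number of CRC cases will be tracked by unblinded study members at the CRO to determine when to stop enrollment" and "Enrollment will be arrested when a sufficient number of confirmed cases of colorectal cancer have been identified among the cohort to achieve study endpoints". SAP 6 places the count at pathology review of the colonoscopy reports.

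**The concern.** Two quantities are each used in place of another.

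- **Yield.** A probability that is true of participants who reach the analysis is quoted for participants who have only consented. A reader planning from it would expect too many cases from the first 8,500.
- **Stopping count.** The number that ends enrollment is confirmed cancers. The number tested against the CRC criterion is confirmed cancers with a valid mt-sRNA score. If some cancers have no valid score, recruitment can stop at 48 with fewer than 48 in the analysis. The blocks of 1,000 do not repair this, because the same count triggers them.

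The second matters because the criterion is stepped. With 48 cases, 4 misses pass (exact lower limit for 44/48 = 80.02%). With 47 cases, 4 misses fail (43/47 = 79.62%) and only 3 are allowed.

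**Working it through.** **Inputs from the documents.** Prevalence 0.6%, first tranche 8,500, target 48 cases, blocks of 1,000 (Protocol 3.5); about 14,000 consented (SAP 7.1); CRC estimate above 90% with exact lower limit above 80% (Protocol 2.1, SAP 4.2.1). True sensitivity of 95% follows the 19 of 20 in Protocol 1.2. **Assumptions:** all evaluable shares and loss rates, since the documents give none. Evaluable shares are applied equally to cancers.

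**Step 1. Reproduce the plan's figure.** P(X ≥ 48) for X ~ Binomial(8,500, 0.006), mean 51.0, is 0.682. The stated 68% is correct for 8,500 people who all contribute an analysable outcome.

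**Step 2. First tranche with losses.** With evaluable share s, use Binomial(8,500 × s, 0.006):

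| s (assumed) | Evaluable | Expected CRC | P(≥ 48) |
|---|---|---|---|
| 100% | 8,500 | 51.0 | 68% |
| 95% | 8,075 | 48.5 | 55% |
| 90% | 7,650 | 45.9 | 40% |
| 80% | 6,800 | 40.8 | 15% |

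**Step 3. The same calculation for 14,000 consented.**

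| s (assumed) | Evaluable | Expected CRC | P(≥ 48) |
|---|---|---|---|
| 80% | 11,200 | 67.2 | 99% |
| 70% | 9,800 | 58.8 | 93% |
| 60% | 8,400 | 50.4 | 65% |

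**Step 4. The stopping rule as written.** Let c be the share of recruits who complete colonoscopy. Draw confirmed cases from Binomial(8,500, 0.006c). While the total is below 48, add Binomial(1,000, 0.006c). Then remove each confirmed case with probability λ, the share without a valid mt-sRNA result. The distribution was computed exactly by recursion. Mean confirmed cases at the stop are 53.7 for c = 100% (exactly 48 in 9%) and 50.6 for c = 80% (exactly 48 in 20%).

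Power is the sum over usable case numbers u of P(u) × P(misses ≤ m(u)), with misses ~ Binomial(u, 0.05). The allowed misses m(u) are 3 for 41–47 cases, 4 for 48–54 and 5 for 55–61.

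| λ (assumed) | P(< 48 usable), c = 100% | Power, c = 100% | P(< 48 usable), c = 80% | Power, c = 80% |
|---|---|---|---|---|
| 0 | 0% | 91% | 0% | 90% |
| 1% | 4% | 90% | 9% | 89% |
| 2% | 9% | 90% | 19% | 88% |
| 5% | 24% | 88% | 45% | 86% |

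The chance of missing 48 usable cases can be large, but the power loss is only about 1 to 4 points. The rule usually overshoots 48, and within a step such as 48–54, losing a case slightly raises power (87% at 54 cases, 91% at 48).

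**The case against.** **The extension rule and the actual enrollment overtake the first-tranche figure.** This largely stands. A shortfall at 8,500 leads to more recruitment, and Step 3 shows that 14,000 consented makes 48 evaluable cases likely unless the evaluable share is low. The 55/40/15% therefore describes how the figure was stated and does not forecast the trial's outcome.

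**The protocol may already mean analysable cases.** It refers to achieving the endpoints and adds: "Enrollment will continue until all endpoints are fully powered". Its counters are described as unblinded. That reading is possible, but no text makes a valid score part of the count. The SAP points the other way: the count is taken from colonoscopy reports, laboratory and colonoscopy eligibility are determined separately (SAP 7.2), and people with colonoscopy access are blinded to laboratory information (SAP 5.3). The CRO is told of samples that fail on receipt (Protocol 5.2 and 5.3), but no rule ties that notice to the count.

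**Safeguards keep losses among cancers small.** This stands in part. Collection can be repeated (Protocol 5.2 and 5.11, SAP 8.1), and a second replicate is run after an invalid result (SAP 7.6). Cancers are kept despite a limited colonoscopy (Protocol 5.7) or unclear reports (Protocol 5.9). These measures lower the loss rates but do not define the count.

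**Stronger readings that the documents do not support.** A reader might infer that the study is underpowered, or that 14,000 consented proves heavy attrition. The documents give neither the evaluable number nor the reason for 14,000. Lower prevalence, delay in retrieving records, over-enrollment or attrition could each explain it. Nor is the 68% a miscalculation. The criterion applies to whatever number is evaluable, so neither bias nor a type I error problem follows.

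**Conclusion.** The point holds as a fault in what the figure is attached to and in how the required cases are defined. It is worth correcting, with a minor to moderate effect. The 68% belongs to 8,500 evaluable participants and falls to 55/40/15% at assumed evaluable shares of 95/90/80%. The count that ends enrollment is not, as written, the count that enters the CRC analysis. The cost of that mismatch is about 1 to 4 points of power at true 95% sensitivity, 0.6% prevalence and 1 to 5% invalid results among confirmed cancers. The direction follows from the documents. The size rests on assumed rates, and the safeguards above may make it smaller.

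**What to change.** In Protocol 3.5 and SAP 6:

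1. State that the 68% applies to 8,500 evaluable participants, meaning those with a valid mt-sRNA result and a valid colonoscopy category. Give its value over a range of assumed evaluable shares, for example 55/40/15% at 95/90/80%.
2. Define the required number of CRC cases as confirmed CRC with a valid mt-sRNA result.

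Enrollment closed in June 2022 (SAP 7.1), so no stopping rule is left to run and no new exchange between laboratory and CRO is needed. Take the evaluable CRC count from the two locked eligibility determinations (SAP 7.2). Report it in the clinical study report against the existing false-negative table (Protocol Table 2, SAP Table 3).

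The cost is a few sentences in each document and a less favourable stated figure. Blinding, the separate data locks and the primary analysis are unchanged, and no participants are added.

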#### 3.5 Primary Statistical Analysis Plan

A variety of categorical data analysis methods will be used to analyze the results from the mt-sRNA test and the reference colonoscopy results. Binomial proportions together with exact 95% confidence intervals will be used to summarize sensitivity and specificity for various categories. Fisher exact tests will be used for determining whether there are significant differences in assay performance between various subgroups, e.g., are there differences in sensitivity for CRC between females and males. If there are statistically significant ( $\alpha$ =0.05) differences observed, logistic regression will be used to perform any modeling to better understand differences.

**Table 3.** Data summaries will be generated for demographic and risk characteristics.

Demographics	Total % (n)	CRC % (n)	AA % (n)	OA % (n)	Specificity% (n)
Age 45-55 55-65 65-75 75+	x (xx)	x (xx)	x (xx)	x (xx)	x (xx)
Smoking	x (xx)	x (xx)	x (xx)	x (xx)	x (xx)

Title: CRC-PREVENT Clinical Validation Protocol

**Document Number: VAL-PRT-0041** 

Never smoked Previous smoker Currently smoke					
Sex Female Male No Answer	x (xx)				
Family History of CRC No Yes	x (xx)				
Ethnic Background American Indian / Alaska Native African American / Black Asian White Native Hawaiian / Pacific Islander Other Prefer not to answer	x (xx)				
Race Hispanic Non-Hispanic Other Prefer not to answer					
Average Income \$200,000 or More \$150,000-\$199,999 \$100,000-\$149,999 \$75,000-\$99,999 \$50,000-\$74,999 \$30,000-\$49,999 Under \$29,999 Prefer not to answer	x (xx)				
Insurance No Insurance Private Insurance Public Insurance (Medicaid) Public Insurance (Medicare Advantage) Public Insurance (Medicare) Self-Insured	x (xx)				
Geographic Rural Urban / Suburban	x (xx)				

CENEOCCODY INC	Title: CRC-PREVENT Clinical Validation Protocol
GENEOSCOPY, INC.	Document Number: VAL-PRT-0041

TO III 4 D		C 11	1	111 1	. 1	•	C . 1.1
Table 4 Data	summaries 1	tor all	subjects	Will be	siimmarized	1n a	frequency table:

Mt-sRNA Test	His	Histopathological Lesion Category Grouping				
Result	CRC	AA	OA	Negative	Total	
Positive	a	ь	С	d	a+b+c+d	
Negative	e	f	g	h	e+f+g+h	
Total	a+e	b+f	c+g	d+h	N	

The primary endpoint metrics will be calculated as:

- mt-sRNA test sensitivity for subjects with CRC = a / (a+e)
- mt-sRNA test sensitivity for subjects with AA = b / (b+f)
- mt-sRNA test specificity for subjects with negative findings = h/(d+f)

For each of these metrics, the two-sided 95% exact binomial confidence intervals will be provided, and the lower 95% confidence limits will be compared to the acceptance criterion. An additional sensitivity calculation will be presented for subjects with Other Adenomas.

• mt-sRNA test sensitivity for subjects with OA = c/(c+g)

The two-sided 95% confidence interval will be calculated for this metric although there is no specific acceptance criterion against which it will be compared.

#### 3.6 Additional Metrics of mt-sRNA test Performance

Using the data from the above tables, the positive predictive value (PPV) for various clinical outcomes and the negative predictive value (NPV) will be calculated as follows, assuming underlying prevalences of the various disease categories that match those observed in the clinical study:

- PPV (CRC) = Probability of having CRC given a positive mt-sRNA test result = a / (a+b+c+d)
- PPV (AA) = Probability of having AA given a positive mt-sRNA test result = b / (a+b+c+d)
- NPV = Probability of having negative findings on Colonoscopy given a negative mt-sRNA test Result = h / (e+f+g+h)

The above straightforward calculations are possible under the assumption that underlying disease prevalences observed in the clinical validation study match real-world prevalences. In the event that observed prevalences differ from expected prevalences, PPV and NPV calculations will also be performed for alternative assumed prevalences. In that case, PPV and NPV will be calculated by Bayes theorem using the alternative assumed prevalences together with the study estimates of the sensitivity and specificity components.

An alternative characterization of diagnostic performance can be made via diagnostic likelihood ratios (DLRs), which indicate how much greater the odds are that a subject has or does not have the condition once the test result is available.

Three DLRs will be calculated:

- positive DLR (CC) = P(Test positive | CRC) / P(test positive | No CRC) = a / (b+c+d)
- positive DLR (AA or CC) = P(Test positive | AA or CC) / P(test positive | No AA nor CC) = (a+b) / (c+d)

Title: CRC-PREVENT Clinical Validation Protocol

**Table 7. Performance Characteristics by Sex** 

Gender		Crossificites		
	CRC	AA	OA	Specificity
Female	n/N (%)			
Male				
No Answer				
p-value				

Table 8. Performance Characteristics by Ethnic Background

Ethnia Daalagraund		C		
Ethnic Background	CRC	AA	OA	Specificity
African American	n/N (%)			
Asian				
Hispanic / non- white				
White				
Other				
Prefer not to answer				
p-value				

Table 9. Performance Characteristics by Other Precancerous Adenoma Subtype

Subtype	OPA Sensitivity	Specificity
Category 3.0	n/N (%)	

GENEOSCOPY, INC.
------------------

**Document Number: VAL-PRT-0041** 

Category 4.0	
Category 5.0	

Table 10. Performance Characteristics by Advanced Adenoma Subtype

Subtype	AA Sensitivity	Specificity
Category 2.1	n/N (%)	
Category 2.2		
Category 2.3		
Category 2.4		

**Table 11. Performance Characteristics by Cancer Stage** 

Stage	CRC Sensitivity	Specificity
Stage 0	n/N (%)	
Stage I		
Stage II		
Stage III		
Stage IV		

If any differences are noted between any categories in the subgroup analyses, logistic regression will be used for further exploration to understand the cause of the differences.

#### 4. Registration Procedures

#### 4.1 Methods for Engagement

Initial study eligibility will be determined by an online screener provided by the CRO. The advertisement will inform participants about the study and provide basic information on what the study entails. Selection of the advertisement will direct participants to the survey landing page. Gastroenterologists and other individuals on this protocol can also refer participants to this survey landing page. The survey is a series of questions that preliminarily determines if the participant is eligible for the study. The survey interface provides the participant with one question at a time and can be visualized on any computer or smartphone.

# 4.2 Pre-Engagement

To recruit the patient volume and demographic representation needed for this study, patient identification efforts have been conducted prior to the official enrollment period. Engagement with human subjects during preenrollment was regulated under a previously approved IRB (Pro00032825). Beginning in August 2020, participants arrived at a survey landing page for the study and participants had the option to answer a series of questions collecting qualifying information for a follow up phone call from a call center. Patients who qualified for this follow up phone call were contacted to confirm their responses to the online survey, as well as their permission to receive communications leading up to, and during, the enrollment period.

Title: CRC-PREVENT Clinical Validation Protocol

**Document Number: VAL-PRT-0041** 

The CRO recruited patients through advertisements placed on social media platforms. The advertisements informed participants that a clinical study is seeking eligible participants for future enrollment. Selection of the advertisement directed participants to the survey landing page and provided the participants with questions assessing future eligibility. If a participant was disqualified at this time, then the participant was redirected to a thank you page with no further planned communication. However, if a subject qualified, the participant was redirected to a thank you page, received a thank you email, and received a call from a representative with the CRO call center. The qualification and interest of participants was confirmed during this call, which triggered a series of communications that occur prior to the enrollment period. These communications include emails, text messages, newsletters, phone calls and other methods of electronic communication, as required. Participants are always provided an opportunity to opt-out of further communications at any point during this pre-enrollment phase. Once enrollment begins for this study protocol, participants will receive further details about the study and have an opportunity to provide verbal consent for continued participation.

During the previous study (Pro00032825), there were some participants who were not qualified or not able to participate at the time, however they expressed interest in receiving communications about future studies. These subjects will enter the same communication workflow described above.

